5.1.2 Arm B

Six patients enrolled to this study will be in Arm B; patients may be enrolled to Arm B at any time throughout the lifetime of the study. Arm B patients will undergo MLA and will begin doxorubicin (as described in Section 5.4) within approximately 7 days following MLA (range 2-14 days)

Arm B patients will undergo DSC and DCE-MRI at the following time points along with standard of care imaging:

- no more than 3 weeks prior to MLA (OPTIONAL)
- within approximately 4 days after MLA
- 2-4 weeks after MLA
- every 8 weeks (+/- 7 days) until 2 years have elapsed or disease progression (see Section 9.1), whichever comes first

Arm B patients will have 7 mL blood drawn at the following time points:

- before MLA; this sample can be collected any time during the 3 days before or the day of the procedure until the start of the procedure
- within approximately 3 days after MLA
- weekly (+/- 3 days) before (on the same day as) chemotherapy for the 6 weeks post-MLA
- every 8 weeks (+/- 7 days) at time points correlating with MRIs for the first 2 years or until disease progression, whichever comes first

The purpose of these blood draws is to measure serum levels of brain-specific factors (S100B, GFAP, and BSE) and cytokine levels. PBMC (for the pre- and post-MLA samples) will also be isolated to determine the phenotypes and functions of peripheral blood immune cells following MLA (see Section 9.2 -9.4). This is in addition to blood samples for routine laboratory prior to chemotherapy and surgery. During the weeks of DSC/DCE-MRI, biomarker lab must be drawn on the same day as DSC/DCE-MRI (prior to the scan).

5.2 MRI-Guided Laser Ablation

MLA is a minimally invasive laser surgery currently FDA approved for cytoreductive treatment of brain tumors, both primary and metastatic [25]. MLA employs a small incision in the scalp and skull, through which a thin laser probe is inserted and guided by MR imaging to the core of a tumor mass where it delivers hyperthermic ablation from the core to the rim. The maximal temperature in the core can reach greater than 70°C resulting in coagulative necrosis.

5.3 Premedication Administration

Because doxorubicin is emetogenic, prophylactic use of antiemetics will be used.

5.4 Agent Administration

Arm B only: Doxorubicin will be given intravenously on an outpatient basis weekly for 6 weeks at a dose of 25 mg/m² over 5-30 minutes. Doxorubicin will be held for an ANC of <500/mcl or platelets <50 K/cumm. Following the 6 weeks of doxorubicin, etoposide at 50 mg/m²/day will be given orally for 21 days of each 28-day cycle to begin once ANC ≥ 1000/mcl and platelets ≥ 100 K/cumm. Etoposide will be held for ANC of < 500/mcl or platelets < 50 K/cumm. Patients may receive up to 24 cycles of etoposide.

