5.6 General Concomitant Medication and Supportive Care Guidelines

Subjects in Arm B should not receive medications that may interact with doxorubicin or etoposide. Refer to the product labels for details. Therapies excluded during the conduct of this trial include in Arm B include other chemotherapy agents, hormonal therapy for cancer, and other tumor-targeted therapies including but not limited to radiotherapy. Therapeutic use of hematopoietic colony-stimulating factors is permitted following for ANC < 500/mcl and should not be given within 24 hours prior to or following doxorubicin.

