6.0 DOSE DELAYS/DOSE MODIFICATIONS (ARM B)

The following algorithms are meant as guidelines only; adjustments to chemotherapy may be made at the discretion of the treating physician.

Renal Dysfunction:

CrCl 10 to 50 ml/min: administer 75% of etoposide dose

CrCl <10ml/min: administer 50% of etoposide dose

Congestive heart failure:

Given the low dose and short duration of doxorubicin treatment, we do not anticipate significant cardiac toxicity. However, if a prolongation of the QTc interval (>0.48 sec), a decrease in ejection fraction to <50%, or a decrease in left ventricular shortening fraction to <27%, doxorubicin should be omitted one week, any existing electrolyte or micronutrient deficiencies corrected, and the tests repeated. If the abnormalities persist, doxorubicin treatment should be permanently discontinued. Missed doses due to cardiac toxicity will not be made up.

Hematologic abnormalities:

Hold etoposide for ANC <500/mcl or platelet < 50 K/cumm. May restart when ANC ≥ 1000/mcl and platelet > 100 K/cumm. Etoposide may be restarted at full dose or reduced dose at the discretion of the treating physician. Missed doses will not be made up.

Baseline Permissible ANC	Subsequent ANC	Growth Factor Support, Treatment Delay and Follow-up Labs	Dose Reduction of Doxorubicin Based on Rates of Abnormal Lab Recovery
ANC ≥ 1000/mcl	ANC ≥ 1000/mcl	None	None
	ANC < 1000/mcl but > 500/mcl	G-CSF 5 mcg/kg SQ or IV qday x up to 5 days. Check CBC daily. When ANC ≥ 1000/mcl, restart treatment.	None if ANC recovers to ≥ 1000/mcl within 5 doses of G-CSF.
			Decrease to 20 mg/m ² if ANC recovers to ≥ 1000/mcl after 5 doses of G-CSF.
			Decrease to 15 mg/m ² if ANC takes > 14 days to become permissible.
	ANC < 500/mcl	G-CSF 5 mcg/kg SQ or IV qday x up to 5 days. Check CBC daily. When ANC ≥ 1000/mcl, restart treatment.	Decrease to 20 mg/m ² if ANC recovers to ≥ 1000/mcl within 5 doses of G-CSF.
			Decrease to 15 mg/m ² if ANC recovers to ≥ 1000/mcl after 5 doses of G-CSF.
Discontinue treatment if ANC takes > 21 days to become permissible.			

Baseline Permissible Platelets	Subsequent Platelet count	Treatment Delay and Follow-up lab§	Dose Reduction of Doxorubicin Based on Rates of Abnormal Lab Recovery
Platelet \geq 100 K/cumm	Plt \geq 50 K/cumm	None	None

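### For an ANC between 500 and 1000/mcl, Sections 5.4, 5.6 and 6.0 give conflicting instructions on doxorubicin and G-CSF

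*Combined protocol and SAP*

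**What the plan says.** Three places govern neutrophil counts during doxorubicin in Arm B.

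- **Section 5.4** states: "Doxorubicin will be held for an ANC of <500/mcl or platelets <50 K/cumm". It names no other neutrophil trigger for doxorubicin and gives no count at which doxorubicin resumes.
- **Section 6.0**, in the doxorubicin ANC table, has a row for "ANC < 1000/mcl but > 500/mcl". The action is: "G-CSF 5 mcg/kg SQ or IV qday x up to 5 days. Check CBC daily. When ANC ≥ 1000/mcl, restart treatment". Three dose outcomes follow. There is no reduction if the count reaches 1000 within five G-CSF doses, and a decrease to 20 mg/m² if it gets there after five. The third is: "Decrease to 15 mg/m ² if ANC takes > 14 days to become permissible". The row for counts below 500 has the same action text but its own dose steps. The section opens by calling its algorithms guidance and leaving adjustments to the treating physician.
- **Section 5.6** states: "Therapeutic use of hematopoietic colony-stimulating factors is permitted following for ANC < 500/mcl". The rest of the sentence keeps such use at least 24 hours away from doxorubicin in either direction. Words seem to be missing or misplaced in the quoted part.

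**The concern.** A count between 500 and 1000 on a dosing day is covered by both Section 5.4 and the Section 6.0 table, and they point in different directions. The Arm B calendar (Section 10.2) schedules a CBC in each of the six doxorubicin weeks, so the question can arise repeatedly in one patient.

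Two things are at stake. The first is safety: whether a child with a count in this band receives chemotherapy that day, and whether G-CSF is given, depends on the page consulted. The second is exposure. Section 1.5 explains the weekly schedule as continuous treatment during the presumed six-week period of barrier disruption after MLA. Delay or reduction changes how much drug is given in that period. Arm B has six patients, so inconsistent handling of even one or two would make it harder to describe the regimen behind the 6PFS estimate.

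**Working it through.** The plan states no figure to reproduce. The check sets the three sections side by side by ANC band.

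| ANC (/mcl) | Section 5.4 | Section 6.0 table | Section 5.6 |
|---|---|---|---|
| 1000 or more | no hold | no action | G-CSF condition not met |
| between 500 and 1000 | no hold | G-CSF; restart at 1000 or more; dose may fall | G-CSF condition not met |
| exactly 500 | no hold | no row applies | G-CSF condition not met |
| below 500 | hold | G-CSF; restart at 1000 or more; dose falls | G-CSF permitted |

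The sections are compatible in the top and bottom bands. Between 500 and 1000 there are two mismatches: continue or interrupt (5.4 against 6.0), and whether G-CSF is covered (5.6 against 6.0). At exactly 500 the table is silent.

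**Does the middle row mean interruption?** It does not use the word hold, so this is an inference, but a well-supported one:
- "When ANC ≥ 1000/mcl, restart treatment" presupposes that treatment has stopped.
- The column containing the action is headed as covering treatment delay.
- The dose outcomes depend on how long recovery takes, including a step for more than 14 days.
- The action text is the same as in the row below 500, where Section 5.4 does require a hold.

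**Is it a general pattern?** No. For doxorubicin platelets, Section 5.4 and the table both hold below 50 K/cumm. For etoposide, both sections hold at ANC below 500/mcl or platelets below 50 K/cumm. Among these hold thresholds, only the doxorubicin ANC rule differs.

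**Illustration of cumulative dose.** Inputs: 25 mg/m² weekly for 6 weeks (Section 5.4); 20 and 15 mg/m² (Section 6.0, middle row). Assumptions: any reduction applies from dose 2 onward, and all six doses are given.

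- No reduction: 6 × 25 = 150 mg/m², 0% lower.
- Reduced to 20: 25 + 5 × 20 = 125 mg/m²; (150 − 125)/150 = 16.7% lower.
- Reduced to 15: 25 + 5 × 15 = 100 mg/m²; (150 − 100)/150 = 33.3% lower.

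Under Section 5.4 alone, the same counts lead to no hold, and that section contains no dose reduction.

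**The case against.** The best defence is that the sections sit in a hierarchy: Section 5.4 sets the mandatory hold, and Section 6.0, which describes itself as guidance, offers optional management above it. Section 5.6 is also headed as guidelines, so it need not be read as a strict rule. This is a possible reading, but no text states it. The discretion sentence in Section 6.0 lets the physician adjust chemotherapy; it does not say whether 5.4 or the table governs when they differ. The G-CSF allowance in Arm B inclusion criterion 9a concerns entry laboratory values and does not settle on-treatment use.

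Several limits on the point do stand:

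- A reader might infer that 5.4 forbids a hold above 500, or that 5.6 forbids G-CSF there. Neither section contains the word only or a prohibition; each simply names below 500 as its condition. Because the 5.6 sentence is garbled, the G-CSF mismatch is weaker evidence than the mismatch between 5.4 and 6.0.
- A reader might take 17% to 33% as the expected loss of dose. The first outcome in the disputed row is no reduction, so the range starts at 0%. The protocol also does not say whether doxorubicin doses delayed for neutropenia are made up.
- A reader might infer that patients would be lost from the efficacy-evaluable set. Section 5.5 needs only two doxorubicin doses, and the ANC table discontinues treatment only when recovery takes more than 21 days. Nothing in the documents suggests that a count in this band would commonly prevent a second dose.
- A reader might conclude that one threshold must serve for hold, G-CSF and restart. The documents do not support that: Section 6.0 holds etoposide below 500 and restarts it at 1000 or more, so separate thresholds are not in themselves a contradiction.
- The gap at exactly 500 is minor, since 5.4 gives no hold there.

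**Conclusion.** Wrong as written: an internal inconsistency. For an ANC between 500 and 1000/mcl, one section triggers no doxorubicin hold, while another gives G-CSF, implies interruption until 1000 and may lower the dose. The permission for colony-stimulating factors in a third section does not extend to that G-CSF step. The protocol does not say which section prevails.

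The conflict over hold or continue rests on reading the table row as an interruption, which its wording strongly supports. The G-CSF conflict rests on an unclear sentence and is stated with less force. The illustrated effect on cumulative dose is 0% to 33% (150, 125 or 100 mg/m²) under the assumptions given. It is a range of possible cases, not an estimate, because the documents give no frequency for counts in this band or for slow recovery. An effect on efficacy evaluability is not established. No view is taken on which instruction is clinically right.

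**What to change.** Reconcile Sections 5.4, 5.6 and 6.0 so that they give the same doxorubicin and G-CSF instruction for every ANC value, including exactly 500. Repair the unclear sentence in Section 5.6. State which section governs if a difference remains, and how the discretion sentence in Section 6.0 relates to the hold in Section 5.4. The choice of thresholds and actions belongs to the sponsor's clinical team.

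The cost is amendment wording. Resolving these passages does not in itself require a change to the sample size, assessment schedule or analysis.

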5.5 Evaluability Criteria

All patients are evaluable for toxicity. Patients are evaluated from first receiving study treatment until a 30-day follow up after the conclusion of treatment or death. Patients on Arm A will be followed for a minimum of 6 months or death.

All patients in Arms B are evaluable for efficacy after receiving at least 2 doses of doxorubicin.

5.6 General Concomitant Medication and Supportive Care Guidelines

Subjects in Arm B should not receive medications that may interact with doxorubicin or etoposide. Refer to the product labels for details. Therapies excluded during the conduct of this trial include in Arm B include other chemotherapy agents, hormonal therapy for cancer, and other tumor-targeted therapies including but not limited to radiotherapy. Therapeutic use of hematopoietic colony-stimulating factors is permitted following for ANC < 500/mcl and should not be given within 24 hours prior to or following doxorubicin.

5.7 Women of Childbearing Potential

Women of childbearing potential (defined as women with regular menses, women with amenorrhea, women with irregular cycles, women using a contraceptive method that precludes withdrawal bleeding, and women who have had a tubal ligation) are required to have a negative serum pregnancy test within 14 days prior to MLA.

Female and male patients (along with their female partners) are required to use two forms of acceptable contraception, including one barrier method, during participation in the study and for 2 months following the last dose of chemotherapy.

If a patient is suspected to be pregnant, chemotherapy should be immediately discontinued. In addition a positive urine test must be confirmed by a serum pregnancy test. If it is confirmed that the patient is not pregnant, the patient may resume dosing.

If a female patient or female partner of a male patient becomes pregnant during therapy or within 2 months after the last dose of chemotherapy, the investigator must be notified in order to facilitate outcome follow-up.

5.8 Duration of Therapy

If at any time the constraints of this protocol are considered to be detrimental to the patient's health and/or the patient no longer wishes to continue protocol therapy, the protocol therapy should be discontinued and the reason(s) for discontinuation documented in the case report forms.

In the absence of treatment delays due to adverse events, treatment on Arm B with etoposide may continue for 2 years or until one of the following criteria applies:

- Documented and confirmed disease progression
- Death
- Adverse event(s) that, in the judgment of the investigator, may cause severe or permanent harm or which rule out continuation of study drug
- General or specific changes in the patient's condition render the patient unacceptable for further treatment in the judgment of the investigator
- Suspected pregnancy
- Serious non-compliance with the study protocol
- Lost to follow-up
- Patient withdraws consent
- Investigator removes the patient from study
- The Siteman Cancer Center decides to close the study

Patients who prematurely discontinue treatment for any reason will be followed as indicated in the study calendar.

5.9 Duration of Follow-up

Patients in Arm A will be followed every 12 weeks after the 6-week (or 10-week if done) post-MLA scan until 1 year has elapsed since patient registration or until death, whichever occurs first. Following the first year, patients will continue to be followed every 6 months or at event occurrence for 5 years after patient registration or until death, whichever occurs first. Patients in Arm B will be followed every 8 weeks after the 6-week (or 10-week if done) post-MLA scan until 2 years have elapsed since patient registration or until progression, whichever occurs first. Following the first two years, patients will continue to be followed every 6 months or at event occurrence for 5 years after patient registration or until death, whichever occurs first. Follow-up consists of collection of Karnofsky performance status, DSC/DCE-MRI, and blood for biomarkers until disease progression (or 2 years of elapsed since patient registration or death, whichever occurs first). After documented disease progression, vital status and subsequent treatment will be obtained every 12 weeks for the remainder of the 2 years or until death, whichever occurs first. Patients removed from study for unacceptable adverse events that are possibly, probably, or definitely related to study procedures will be followed until resolution or stabilization of the adverse event. "Stabilization" is defined as remaining at a consistent CTCAE version 4.0 grade of the event for two consecutive assessments.

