9.0 CORRELATIVE STUDIES

9.1 DCE and DSC-MRI

All patients will undergo DSC and DCE-MRI at the following time points:

- no more than 3 weeks prior to MLA (OPTIONAL)
- within approximately 4 days after MLA
- 2-4 weeks (+/- 3 days) after MLA
- Every 12 weeks (+/- 7 days) following the last MRI for the first year or until disease progression for Arm A; every 8 weeks (+/- 7 days) until 2 years have elapsed or until disease progression, whichever comes first, for Arm B.

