10.0 STUDY CALENDAR

10.1 Arm A Study Calendar

	Baseline ¹	MLA	3 Days Post-MLA	2-4 Weeks Post-MLA	Every 12 Wks Thereafter for 12 months Post-MLA ⁴	F/U ¹⁰
Informed consent	X					
Medical history	X					
Physical exam incl. wt	X		X ³	X	X ⁹	X ¹¹
Karnofsky/Lansky	X		X	X	X ⁹	X ¹¹
CBC	X					
CMP	X					
Urine or serum β HCG	X ⁷					
MRI with DCE/DSC	X ⁸		X ²	X ²	X ⁹	X ¹¹
Biopsy		X ⁸				
Blood to measure brain-specific factors (Sections 9.2-9.4)	X		X ²	X ²	X ⁹	X ¹¹
Adverse event assessment ⁵		X	X	X	X	X

1. No more than 21 days prior to MLA.

2. +/- 3 days

3. Weight not required

4. Patients will be followed every 12 weeks from the Week 4 MRI until 1 year has elapsed since MLA or progression, whichever occurs first. After progression, vital status and subsequent treatment will be recorded.

5. Through one year or off protocol.

6. To be obtained with MRI.

7. Females of childbearing potential

8. Optional

9. +/- 7 days

10. F/U every 6 months or at event occurrence for 5 years or until death, whichever occurs first

11. +/- 2 weeks

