10.2 Arm B Study Calendar

	B/L ¹	MLA	3 Days Post-MLA	Wk 1 ⁴	Wk 2 ⁴	Wk 3 ⁴	Wk 4 ⁴	Wk 5 ⁴	Wk 6 ⁴	Monthly ⁵	F/U ¹⁰
Informed consent	X										
Medical history	X									X	
Physical exam incl. wt	X			X	X	X	X	X	X	X	X ¹⁵
Karnofsky/Lansky	X			X	X	X	X	X	X	X	X ¹⁵
CBC	X			X	X	X	X	X	X	X	
CMP	X			X			X			X	
Urine or serum β HCG	X ¹²										
Echocardiogram	X ²										
MRI with DCE/DSC	X ¹⁴		X		X ¹¹					X ^{5,6}	
Biopsy		X ¹⁴									
Blood to measure brain-specific factors (Section 9.2-9.4)		X ³	X	X ⁷	X ⁷	X ⁷	X ⁷	X ⁷	X ⁷	X ^{5,6}	
Doxorubicin ⁸				X	X	X	X	X	X		
Etoposide ¹³										X	
AE assessment ⁹		X	-----								X

1. No more than 21 days prior to MLA.

2. No more than 1 year prior to registration.

3. May be collected any time during the 3 days before or the day of the procedure until the start of the procedure.

4. +/- 3 days

5. +/- 7 days

6. Every 8 weeks for the first 2 years or until disease progression, whichever occurs first. To coincide with MRI. After progression, vital status and subsequent treatment will be recorded.

7. Same day as chemotherapy.

8. To begin approximately 7 days after MLA.

9. Through one year or off protocol

10. Patients will be followed every 6 months or at event occurrence for 5 years or until death, whichever occurs first.

11. To be obtained 2-4 weeks post-MLA

12. Females of childbearing potential

13. To be started at time of count recovery after the 6 weeks of treatment with doxorubicin has concluded.

14. Optional

15. +/- 2 weeks

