12.0 MEASUREMENT OF EFFECT

12.1 Antitumor Effect – Solid Tumors

For the purposes of this study, patients should be re-evaluated for response every 12 weeks on Arm A and every 8 weeks on Arm B. The DCE/DSC-MRI scan obtained within approximately 3 days after MLA will be used as the baseline scan for determining response. The DCE/DSC-MRI scans obtained at pre-MLA, post-MLA, and prior to 6 weeks post-MLA will not be assessed for disease response.

Response and progression will be evaluated in this study using the updated response assessment criteria for high-grade gliomas: Response Assessment in Neuro-Oncology (RANO) working group guideline [JCO 28(11): 1963-1972, 2010].

Criteria for Determining First Progression Depending on Time From Initial Chemoradiotherapy

First Progression	Definition
Progressive disease < 12 weeks after completion of chemoradiotherapy	
Progression can only be defined using diagnostic imaging if there is new enhancement outside of the radiation field (beyond the high-dose region or 80% isodose line) or if there is unequivocal evidence of viable tumor on histopathologic sampling (eg, solid tumor areas [ie, > 70% tumor cell nuclei in areas], high or progressive increase in MIB-1 proliferation index compared with prior biopsy, or evidence for histologic progression or increased anaplasia in tumor). Note: Given the difficulty of differentiating true progression from pseudoprogression, clinical decline alone, in the absence of radiographic or histologic confirmation of progression, will not be sufficient for definition of progressive disease in the first 12 weeks after completion of concurrent chemoradiotherapy.

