14.0 STATISTICAL CONSIDERATIONS

Since we do not have any preliminary data for MR imaging, serum biomarkers, etc, it is not feasible to estimate sample size or provide power estimates. Therefore, this study is considered as a pilot study and the data collected will be used to design future studies. We propose six patients each arm as this is considered to be reasonable to recruit within the available a time frame.

In each arm, we will consider the following statistical analysis:

For the primary endpoint, MR imaging will be collected at the time points: pre-MLA (OPTIONAL), post-MLA, two-four weeks after MLA and every twelve weeks in Arm A; pre-MLA, post-MLA, two-four weeks after MLA and every eight weeks in Arm B. The linear regression model will used to investigate the correlation between MR imaging and peritumoral BBB disruption. To account for correlation among the repeated measures from the same patient, the longitudinal data will be analyzed with the use of linear generalized estimating equation (GEE). Whether the average measurements differ at the multiple time points will be evaluated through GEE model. Least-square means at each time points will be presented and standard errors will be calculated within the use of the GEE sandwich method when accounting for within-patient correlation.

Since we do not know which biomarkers will have better correlation with the Ktrans data from DCE and DSC-MRI and patients' survival outcome, we plan to determine the levels of all 3 biomarkers in a blinded fashion. Once both the Ktrans and biomarker levels are available, we will determine which biomarkers have the closest correlation that is statistically significant with the Ktrans. Pearson correlation coefficient (r) will be determined for each biomarker and Ktrans value. Biomarkers with higher correlation coefficient (r approaching 1) will be given higher priority. A minimum $r=0.5$ is required for inclusion for further analysis and will be used as a peritumoral

permeability score. This score will then be correlated with the patient outcome data (as measured by 6PFS rate) to determine whether it has a predictive value.

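### Section 5.9 counts follow-up scans from a six- or ten-week scan that no other section schedules, so the Arm B primary 6PFS depends on which section is followed

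*Combined protocol and SAP*

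**What the plan says.** Section 5.9 sets follow-up in both arms relative to a later post-MLA scan. For Arm A: "Patients in Arm A will be followed every 12 weeks after the 6-week (or 10-week if done) post-MLA scan". For Arm B: "Patients in Arm B will be followed every 8 weeks after the 6-week (or 10-week if done) post-MLA scan". It says that follow-up includes DSC/DCE-MRI.

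The other sections differ:

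- **Section 9.1**, Arm A: "Every 12 weeks (+/- 7 days) following the last MRI for the first year or until disease progression for Arm A". Arm B, in the same bullet: "every 8 weeks (+/- 7 days) until 2 years have elapsed or until disease progression, whichever comes first, for Arm B". The preceding bullet is the scan at weeks 2-4.
- **Section 10.1**, footnote 4: "Patients will be followed every 12 weeks from the Week 4 MRI until 1 year has elapsed since MLA or progression".
- **Section 10.2**, footnote 6: "Every 8 weeks for the first 2 years or until disease progression, whichever occurs first. To coincide with MRI". The early scan is at weeks 2-4 (footnote 11), and the Week 6 column has no MRI mark.
- **Section 14**: "pre-MLA, post-MLA, two-four weeks after MLA and every eight weeks in Arm B".
- **Section 12.1** uses six weeks only as a cut-off: "The DCE/DSC-MRI scans obtained at pre-MLA, post-MLA, and prior to 6 weeks post-MLA will not be assessed for disease response".

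Section 12.3.6 measures PFS from the start of treatment to progression or death. Section 5.1.2 puts first doxorubicin about 7 days after MLA, with a range of 2-14 days. Section 14 estimates PFS by Kaplan-Meier and gives 6 months as an example of a reporting time. Section 2.1 makes 6PFS the Arm B primary objective; Sections 2.2 and 14 use it as the outcome for the permeability score.

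**The concern.** Radiological progression can be recorded only when a scan is done. Whether a patient counts as progression-free at 6 months therefore depends on where the scans fall relative to that point and on when the clock starts. The current text fixes neither for Arm B. It refers to a scan that is not scheduled, and it does not say whether treatment starts with MLA or with doxorubicin. Two analysts could follow different sections in good faith and report different values of the same primary endpoint from the same patients, and the choice could be made after the data are seen. Section 14 says that these data will be used to design future studies, so the ambiguity would be carried forward.

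**Working it through.** The plan gives no power, sample-size or expected 6PFS figure to reproduce; six per arm rests on feasibility (Section 14).

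**1. Scan dates, in weeks after MLA.**

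- Arm A: 9.1 (from the week 2-4 scan) gives 14-16, then 26-28. The calendar (from week 4) gives 16, then 28. Section 5.9 gives 6, 18, 30 or 10, 22, 34.
- Arm B: see the table. Counting from the week 2-4 scan is inferred from list order in 5.1.2, 9.1 and 14; it is not stated.

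**2. Start of the clock.** Section 12.1 takes its baseline scan about 3 days after MLA. Section 12.3 wants baseline evaluations before treatment begins and no more than 2 weeks earlier. Together these lean towards doxorubicin. But MLA is the first step of the treatment plan, and the wording in 12.3 is generic. The question stays open.

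**3. Dating.** Section 12.3.4 ends duration of response on the date when progression is first objectively documented. Nothing says that this also applies to PFS.

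**4. Effect of the anchor on Arm B 6PFS.** Assumptions, not from the documents: exponential progression, true 6PFS p = 0.30, clock at MLA, nominal dates, scan-detected progression dated at that scan. Six months is 365.25 / 2 / 7 = 26.09 weeks. S(t) = 0.30^(t/26.09). If a share c of progressions is dated clinically at the true time (12.1 accepts clinical deterioration as progression), the Kaplan-Meier value at 6 months reads c × 0.30 + (1 − c) × S(L), where L is the last scan at or before week 26.09.

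| Anchor | Scan weeks | L | c = 0 | c = 0.3 | c = 0.6 |
|---|---|---|---|---|---|
| Week-2 scan | 10, 18, 26 | 26 | 0.301 | 0.301 | 0.300 |
| Week-3 scan | 11, 19, 27 | 19 | 0.416 | 0.381 | 0.346 |
| Week-4 scan | 12, 20, 28 | 20 | 0.397 | 0.368 | 0.339 |
| 5.9, six-week | 6, 14, 22, 30 | 22 | 0.362 | 0.344 | 0.325 |
| 5.9, ten-week | 10, 18, 26 | 26 | 0.301 | 0.301 | 0.300 |

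For example, 0.30^(19/26.09) = 0.416, and 0.3 × 0.30 + 0.7 × 0.416 = 0.381. The scan-only range is 30-42%. At a true 60% it is 60-69%; at a true 90% it is 90-93%.

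**5. Effect of the clock.** Same model with c = 0, each scan uniform within ±7 days, doxorubicin uniform over days 2-14 (simulated). The 6-month point moves from week 26.1 to between weeks 26.4 and 28.1 after MLA.

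| Anchor | Clock at MLA | Clock at doxorubicin |
|---|---|---|
| Week 2 | 37% | 31% |
| Week 3 | 41% | 34% |
| Week 4 | 40% | 38% |

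The shift is about 2-7 points. The ten-week count of 5.9 shares the week-2 dates. On the six-week count nothing moves, because scans at weeks 21-23 and 29-31 cannot cross the interval 26.1-28.1.

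**6. Scale.** One patient of six is 100 / 6 = 16.7 points; the anchor range is about 42 − 30 = 12. The exact 95% interval for 2/6 is 4-78%.

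**The case against.** The case for leaving the text alone has weight. Section 12.3.6 does give an origin and Section 14 an estimator, so a reader who infers that 6PFS has no clock at all goes too far; only the identity of the starting event is open, over 2-14 days. List order, and the single bullet covering both arms in 9.1, make the week 2-4 scan the likely intended anchor in Arm B. Section 12.3.4 shows how the protocol tends to date progression. Dating at the detecting scan also raises any scan-based Kaplan-Meier estimate, even under one consistent schedule, so the excess over 30% is not all due to the contradiction; what the contradiction adds is the spread between readings. With six patients and no test of 6PFS, that spread is small beside chance.

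Three stronger readings are tempting and not supported:

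- **The clock alone moves 6PFS from 40% to 27%.** This needs the week-4 anchor, doxorubicin on day 14 and exact scan dates, so that week 28 falls just inside week 28.09. With the protocol's ±7 day window the same case goes from 40% to 33%, and at the nominal day 7 it stays at about 39-40%.
- **6PFS could be scored at the first scan after 6 months and read too low.** No passage proposes this.
- **Arm A's primary result is affected in the same way.** Arm A has conflicting anchors, but Section 2.1 gives it PFS and OS, not 6PFS.

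These points limit the size. None removes the contradiction: 5.9 still conflicts with every scan schedule in the protocol, and the inferred Arm B anchor conflicts with the only stated one.

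**Conclusion.** The point stands as a contradiction in the schedule behind the Arm B primary endpoint, together with an unnamed starting event for PFS. Under the stated assumptions the anchor alone moves an assumed true 30% to somewhere between 30% and 42%, less when some progression is detected clinically. The clock moves it by about 2-7 points on the week 2-4 anchors. Each effect is less than one patient of six, and some readings show almost no excess. The documents give no progression rate, so these figures illustrate size and do not predict the result. Severity is low to moderate. It is still worth correcting, because an interval reports sampling error but not a choice between definitions, and the correction is cheap.

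**What to change.** 1. Reconcile 5.9 with 5.1, 9.1, 10, 12.1 and 14, and name one scan anchor per arm.
2. In 12.3.6, name the event that starts the PFS clock in each arm. State that progression is dated at the detecting scan, or at clinical deterioration or death.
3. In Arm B, place one already planned scan nominally at week 26 from that origin, for example 10, 18, 26 and then every 8 weeks.
4. Define 6PFS once, as status at that scan including its ±7 day window, with earlier clinical progression or death counted as an event. Use it in place of the 6-month Kaplan-Meier reading in Section 14, and keep the Kaplan-Meier curves for description.

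Step 4 needs the replacement. On the schedule in step 3 with its window, the 6-month Kaplan-Meier value would still read about 37% at an assumed true 30%, which would leave two 6-month figures side by side. Status at a scan uniform over weeks 25-27 reads 30 / 60 / 90% at a true 30 / 60 / 90%.

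The cost is wording. No scans are added relative to 9.1: with the origin at MLA, weeks 10 to 98 every 8 weeks is (98 − 10) / 8 + 1 = 12 scans over two years, the same as weeks 12 to 100. The downsides are slightly less freedom in scan dates, a first interval that may differ from 8 weeks, and a slightly less favourable figure.
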